GSK	GlaxoSmithKline
HAQ-DI	Health Assessment Questionnaire – Disability Index
ICH E9	International Council for Harmonization Efficacy guideline 9
IDMC	Independent Data Monitoring Committee
IFN	Interferon
IL	Interleukin
IP	Investigational Product
ITT	Intent-to-Treat
MACE	Major Adverse Cardiac Events

MCS	Mental Component Summary
MedDRA	Medical Dictionary for Regulatory Activities
MMRM	Mixed Model for Repeated Measures
NRS	Numeric Rating Scale
P1NP	Procollagen Type 1 N-propeptide
PCI	Potential Clinical Importance
PCS	Physical Component Summary
PD	Pharmacodynamics
PGIC	Patient Global Impression of Change
PH	Proportional Hazards
PK	Pharmacokinetics
PMR	Polymyalgia Rheumatica
PP	Per Protocol
PT	Preferred Term
PhGA	Physician Global Assessment of disease activity
PtGA	Patient Global Assessment of disease activity
PRO	Patient-Reported Outcomes
q2w	Every 2 weeks
q4w	Every 4 weeks
SAE	Serious Adverse Event
SAP	Statistical Analysis Plan
SAS	Statistical Analysis System
SC	Subcutaneous
SD	Standard Deviation
SE	Standard Error
SIQ	Steroid Impact Questionnaire
SF-36v2	36-item Short Form health survey version 2
SMQ	Standardized MedDRA Query
SOC	System Organ Class
TEAE	Treatment-Emergent Adverse Event
TEAESI	Treatment-Emergent Adverse Event of Special Interest

US	Ultrasound
VAS	Visual Analogue Scale

1. Introduction

Sirukumab is a human anti-interleukin (IL)-6 immunoglobulin G1 (IgG1) kappa monoclonal antibody with a high affinity and specificity for binding to the human IL-6 molecule that is being developed for the treatment of giant cell arteritis (GCA).

Multiple lines of evidence support a role for IL-6 in the pathophysiology of GCA. Sirukumab may have therapeutic benefit in the treatment of GCA by interruption of multiple pathogenic pathways. The purpose of this study is to evaluate the efficacy and safety of sirukumab to characterize the benefit-to-risk profile of sirukumab in the treatment of active GCA.

This Statistical Analysis Plan (SAP) is based on the protocol version 3.0 dated of 17th November 2016. This SAP contains definitions of analysis sets, derived variables and statistical methods for the analyses of efficacy and safety endpoints.

[Section 4](#) to [Section 10](#) focus on Part A of this study. Specific derivations for Part B will be presented in [Section 11](#).

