4.6.4. Missing Data Handling Rules

For cases where the baseline data is missing, no imputations will be performed.

GCA formal/suspected diagnosis Imputation Dates:

Time since formal diagnosis is defined as: Randomization date - formal diagnosis date + 1

Time since suspected diagnosis is defined as: Randomization date - suspected diagnosis date + 1

Partial dates for suspected/formal diagnosis recorded in the eCRF will be imputed using the following:

- If the day of suspected diagnosis is missing then day will be set to “01” month.
- If the month of suspected diagnosis is missing then month will be set to “January”.
- If either the day or month is missing for formal diagnosis then the following rules will be applied:

- If the day of formal diagnosis is missing then it will be set to “01” or to the day of suspected diagnosis, only if the year and month of suspected and formal diagnoses are equal – whichever is later.
- If the month of formal diagnosis is missing then it will be set to “January” or to the month of suspected diagnosis, only if the year of suspected and formal diagnoses are equal – whichever is later.

Concomitant Medication and Adverse Events Imputation Dates:

The following method will be used to impute missing dates for concomitant medications and adverse events (AE):

Missing start dates (where UK and UKN indicate unknown or missing day and month, respectively):

- UK-*MMM*-*YYYY*:
 - If the month and year are different from the month and year of first SC IP dose in Part A, assume 01-*MMM*-*YYYY*.
 - If the month and year are the same as the first study dose month and year and the stop/end date (after any imputation) is on or after first SC IP dose in Part A, then assume the date of first SC IP dose in Part A.
 - If the month and year are the same as first SC IP dose in Part A month and year and the stop/end date (after any imputation) is prior to first SC IP dose in Part A, then assume the stop/end date for the start date.
- DD-UKN-*YYYY*/UK-UKN-*YYYY*:
 - If the year is different from the year of first SC IP dose in Part A, assume 01-JAN-*YYYY* of the collected year.
 - If the year is the same as first SC IP dose in Part A year and the end date (after any imputation) is on or after first SC IP dose in Part A, then assume the date of first SC IP dose in Part A.

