9.1. Adverse Events

The definition of an AE is detailed in Section 12.4.1 in Appendix 4 of the protocol.

Treatment-emergent AEs:

A treatment-emergent AE for Part A is defined as an AE with a start date during the exposed period.

The exposed period is defined as the period from the 1st dose of SC IP to:

- Early withdrawal: last dose of SC IP + 16 weeks

- Completers (subjects who attended the week 52 visit):
 - Week 52 visit if entering into part B
 - Last dose of SC IP + 16 weeks if not entering into part B

Unless otherwise specified, AE outputs will be based on TEAEs.

All AEs will be coded by system organ class (SOC) and preferred term (PT) according to the Medical Dictionary for Regulatory Activities (MedDRA, Version 19.0 or higher).

An overview summary of TEAEs, including counts and percentages of subjects will be generated by actual treatment group, with any of the following categories:

- Any TEAE, TEAEs related to study treatment (SC IP and/or prednisone study drug), TEAEs leading to permanent discontinuation of study treatment, TEAEs leading to dose interruption/delay, TEAEs leading to dose reduction, TEAEs leading to dose increase, TEAEs leading to dose not changed.
- Any serious TEAEs, serious TEAEs related to study treatment (SC IP and/or prednisone study drug), fatal serious TEAEs, and fatal serious TEAEs related to study treatment.
- Any TEAE of special interest (TEAESI) (see [section 9.1.8](#) for further details), TEAESIs related to study treatments (SC IP and/or prednisone study drug), TEAESIs leading to permanent discontinuation of study treatment, TEAESIs leading to dose reduction, TEAESIs leading to dose increase, TEAESIs leading to dose not changed, TEAESIs leading to dose interruption/delay.

A listing presenting the relationship between SOC, PT, and AE reported will be provided.

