9.1.1. Incidence of Adverse Events

Summaries of the total number of TEAEs and the number and percentage of subjects with at least 1 TEAE will be provided by actual treatment group and ordered by SOC and PT. This summary will be repeated for pre-study treatment (i.e. AEs starting before the exposed period as defined in [Section 9.1](#)) and post-study treatment AEs (i.e. AEs starting after the exposed period as defined in [Section 9.1](#)).

Treatment-emergent AEs will be presented in descending order from the SOC with the highest total incidence (that is, summed across all treatment groups) to the SOC with the lowest total incidence. If the total incidence for any 2 or more SOCs is equal, the SOCs will be presented in alphabetical order. Within each SOC, the PTs will be presented in alphabetical order. At each level of subject summarization, a subject is counted once if the subject reported 1 or more events.

Common AEs are defined as those reported by more than 5% of the subjects in any of the treatment arm. Summaries of common AEs and common non-serious AEs will be provided (no rounding for the percentage will be used in terms of 5% threshold, e.g. event with 4.9% incidence rate should not be included in this table). The summary will be displayed in descending order of incidence in total column by PT only.

The proportions of subjects with common AEs and relative risks will be summarized for the six comparisons. This will be done using the RELRISK option of the table statement of the SAS PROC FREQ procedure.

Incidences per 100 subject-year will be calculated for the 3 groups of AEs described below, for each SOC and PT. The table will include the number of subjects and AEs, the total subject-years of exposure, the incidence per 100 subject-years of exposure as well as the 95%CI (exact Poisson confidence intervals). For each subject, the duration of exposure is defined as follows:

- For subjects who have an event: from 1st dose of SC IP until the occurrence of the first event.
- For subjects who do not have an event: duration of exposed period.

The exposure-adjusted incidence rates will be calculated for 3 groups of AEs:

- All AESIs (for each category, SOC and PT)
- All fatal serious AEs (for each SOC and PT)
- All SAEs (for each SOC and PT)

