Only demographic and baseline characteristic as well as Safety will be displayed for Part B. All demographic and baseline characteristic as well as Safety summaries produced for Part A will be produced for Part B. Part B outputs will be displayed using the same general layout of Part A outputs, using the same Part A group as the treatment groups.

Each output will be split using a by-line which will contain information on Part B:

- “Never Received OL Sirukumab during Part B” will include all subjects who did not take a dose of Received OL Sirukumab during Part B.
- “Received at Least 1 Dose of OL Sirukumab during Part B” will include all subjects who took at least one dose of OL Sirukumab during Part B.

The Baseline for Part B will be the last measurement done up to and including the Week 52 visit date of Part A.

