11.1.2. Safety – Part B

The Safety – Part B set will include all randomized subjects who received at least 1 dose of SC IP in Part A and entered Part B. All subjects in the Safety – Part B set will be analyzed according to the treatment actually received in Part A and not according to the treatment they were randomized to receive in Part A, in the event there is a discrepancy. The Safety – Part B set will be used to analyze all of the safety endpoints in Part B.

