11.5. Adverse Events

Since some subjects may not take any study drug during Part B, all AEs (not only TEAEs) will be summarized for Part B. An AE for Part B is defined as an AE starting from the Part A Week 52 visit date or the first SC IP of the Part B open-label treatment, whichever is earlier, to the end of study.

All adverse events summary table will be duplicated:

- The first table will use the byline: “Never Received OL Sirukumab during Part B” vs. “Received at Least 1 Dose of OL Sirukumab during Part B”
- The second table will use the following byline:
 - “Exposed” adverse events: Defined as all AEs occurring within 16 weeks after Sirukumab (SC IP or OL Sirukumab intake during Part B)
 - “Non-exposed” adverse events: Defined as all AEs not occurring within 16 weeks after Sirukumab (SC IP or OL Sirukumab intake during Part B)

It is important to note that all adverse events occurring during Part B within 16 weeks after the last intake of SC IP will be considered as “Exposed”, even if a subject never took OL Sirukumab during Part B.

No adverse events leading to discontinuation of study that is related to prednisone study drug will be displayed since prednisone study drug is only taken during Part A. TEAE related to prednisone will be displayed for Part B (instead of related to prednisone study drug for Part A).

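### The SAP has no partial-date rule for the first open-label dose, so a day-unknown adverse event in that month is dated before the dose even if it ends after it

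*SAP*

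**What the plan says.** SAP 4.6.4 sets the start-date imputation for all adverse events and concomitant medications. When only the day is unknown, the month and year are compared with those of the first subcutaneous (SC) dose in Part A. If they match and the event ends on or after that dose, the onset is set to the dose date. "If the month and year are different from the month and year of first SC IP dose in Part A", the onset is set to the 1st, whatever the end date. An unknown end day is set to the last day of the month.

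The SAP Introduction states: "Specific derivations for Part B will be presented in" Section 11. That section contains no date-imputation rule.

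Three definitions use the imputed onset:

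- **Part A treatment-emergent events (SAP 9.1).** The period closes at the "Week 52 visit if entering into part B".
- **Part B events (SAP 11.5).** A Part B event is "an AE starting from the Part A Week 52 visit date or the first SC IP of the Part B open-label treatment", whichever is earlier.
- **Part B exposure by-line (SAP 11.5).** 'Exposed' means within 16 weeks after blinded SC product or open-label sirukumab. 'Non-exposed' is "Defined as all AEs not occurring within 16 weeks after Sirukumab (SC IP or OL Sirukumab intake during Part B"). A note adds that 16 weeks of carry-over from the last blinded injection counts as 'Exposed', even without open-label dosing.

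Columns in the Part B tables do not depend on the onset date. Section 11 presents them "using the same Part A group as the treatment groups", and under 11.1.2 subjects "will be analyzed according to the treatment actually received in Part A".

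**The concern.** The trial has two first doses, and open-label sirukumab may begin at any time in the first 52 weeks of Part B. The SAP treats an ambiguous onset cautiously at the first Part A dose, where it is assumed to follow treatment. At the open-label dose it does the reverse: unless that dose falls on the 1st, the event is placed before it.

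Two tabulations can be affected. For late starters, the 1st may lie beyond the 16-week carry-over, so the event would go under 'Non-exposed'. For subjects who start at Part B entry, the 1st usually precedes the Week 52 visit, so the event becomes a Part A treatment-emergent event and leaves the Part B tables. In Arms D and E it then counts as a placebo event. It can also enter the Part A relative risks, since SAP 9.1.1 states: "The proportions of subjects with common AEs and relative risks will be summarized for the six comparisons", and SAP 9.1.8 plans the same for events of special interest. In Arms A to C it is still counted under sirukumab.

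**Working it through.** There is no plan figure to reproduce. The check applies the written rules to every calendar day of a 365-day year as the first open-label dose.

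**Inputs.** The exposure window is 16 weeks = 112 days (SAP 7.2.1). Let *d* be the day of the month of the first open-label dose and *w* the Part B week of that dose. The last blinded injection is assumed to be at Part A Week 50 (q2w, none missed), with Week 52 as the alternative. Carry-over is counted from the last blinded injection in every arm, as the note in 11.5 says. 'Occurring' is read as onset.

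**Formulas.** The imputed onset lies *d* − 1 days before the dose, and the Week 52 visit 7*w* days before it. The last blinded injection lies *g* days before it, with *g* = 7*w* + 14 (Week 50) or 7*w* (Week 52).

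- Dated into Part A if *d* − 1 > 7*w*.
- 'Non-exposed' if *d* > 1 and *g* − (*d* − 1) > 112.

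**Dated into Part A.** At entry (*w* = 0), every start day except the twelve 1sts qualifies: (365 − 12)/365 = 353/365 = 96.7%. At Week 4, *d* must be 30 or 31: (11 + 7)/365 = 18/365 = 4.9%. At Week 8, *d* − 1 > 56 is impossible, so the share is 0%.

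**Labelled 'Non-exposed'.** At Week 16 with last injection at Week 50, *g* = 126, so *d* runs from 2 to 14: 13 × 12/365 = 156/365 = 42.7%. The other rows follow in the same way.

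| Open-label start (Part B week) | Last injection Week 50 | Last injection Week 52 |
|---|---|---|
| 8 to 14 | 0% | 0% |
| 15 | 72/365 = 19.7% | 0% |
| 16 | 156/365 = 42.7% | 0% |
| 17 | 240/365 = 65.8% | 19.7% |
| 18 | 324/365 = 88.8% | 42.7% |
| 19 | 353/365 = 96.7% | 65.8% |
| 20 | 96.7% | 88.8% |
| 21 to 52 | 96.7% | 96.7% |

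**Example.** Randomised 1 February 2016; last injection 16 January 2017 (Week 50); carry-over ends 8 May 2017; first open-label dose 17 July 2017. An event recorded only as July 2017 is dated 1 July. That is 16 days before the dose and 166 days after the last blinded injection, so it is 'Non-exposed'.

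**Which side of the dose is more often right?** Take the onset day as uniform over the month and the dose day as uniform from the 2nd to month end. Let the event last *L* days, and keep events ending on or after the dose. In a 30-day month, the (dose, onset) pairs with onset on or after the dose number 29 + 28 + … + 1 = 435. For *L* = 7 the pairs kept number 6 × 30 + (29 + 28 + … + 7) = 180 + 414 = 594, giving 435/594 = 73.2%. Over all months the result is 73.5%. For *L* = 14 it is 59.5%. For *L* of 30 or more, or an end day imputed to month end, it is 50.0%. So the present rule puts the onset on the wrong side in 50-74% of these events, and dating to the dose does so in 26-50%.

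**The case against.** The strongest objection concerns wording. SAP 11.5 uses 'starting' to define a Part B event but 'occurring' to define 'Exposed'. The events at issue end on or after the open-label dose, so in ordinary language they occur after it and might already be 'Exposed'. A reader might infer that the SAP certainly labels them 'Non-exposed'; the documents do not establish that. Onset is the more natural reading beside 'starting', but it is an assumption. This stands.

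A reader might also take 50-74% as the share of events mislabelled. It is not. It describes the side of the dose, and for starts at Weeks 8-14 the wrong side changes no label. For events of 30 days or more, or with an imputed end day, the two rules tie. Uniform onset is also unsupported, since late open-label starts follow a flare.

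Practical reach may be nil. A first open-label dose at Part B Week 16 before termination on 10 October 2017 needs randomisation at least 52 + 16 = 68 weeks earlier, by about June 2016, and SAP 1.1 says few subjects completed Week 52. Visits at 2 and 4 weeks after the open-label start, and 24-hour reporting of serious events and several events of special interest, make unknown days likelier for minor events. The Part B tables are descriptive, the by-line for ever having received open-label drug is per subject and does not change for late starters, and every event is listed. All of this limits the importance without removing the inconsistency.

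Finally, a rule placed only in 11.5 would leave the Part A date unchanged and count entry starters' events in both Parts. That is correct and determines where the fix belongs. The Week 52 boundary effect also reaches Part B entrants never given open-label drug; a first-dose rule does not address them.

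**Conclusion.** The gap is real and minor. SAP 4.6.4 ties every partial-start branch to the first Part A dose, and nothing in Section 11 replaces it for the first open-label dose.

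The late-starter result depends on reading 'occurring' as onset, on start dates spread evenly over the calendar, and on the assumed last blinded injection. The effect begins at about Part B Week 15 or 17 under the two injection assumptions and is complete by Week 19 or 21. The entry-starter result (about 97% dated into Part A) needs only the first two of these definitions in SAP 9.1 and 11.5, together with the even spread of start dates.

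A reader might infer that the safety comparison between arms is materially distorted. The documents do not support that: they give no count of partial dates or late starters, the Part B columns remain the Part A arms, and the relative-risk tables are confined to common events and events of special interest. The reason to act is consistency. The present rule is no more often right than the SAP's own first-dose convention, and under the uniform assumptions it is wrong more often for short events.

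**What to change.** In SAP 4.6.4, so that a single imputed date serves both Parts, add: if an adverse event's known month and year equal those of the first open-label dose (and not those of the first Part A dose), and its end date after imputation is on or after that dose, the onset is the first open-label dose date, unless the event was already recorded at a visit before that dose.

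In SAP 11.5, state that 'occurring' means onset. State also that an event dated on the shared Week 52 visit and first open-label dose date is counted once, in Part B if open-label drug was given that day.

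Events with unknown month have the same gap (set to 1 January), but a whole year is too wide to move to a dose date; flag them in the listing.

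The cost is a few SAP sentences and a small programming change before the single database lock. The downside is that some events that began earlier in the month will be counted as exposed, as the SAP already accepts at the first Part A dose.

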4.7. Planned Analyses

Given study termination, only one database lock (DBL) will occur.

5. Subject Disposition

Unless otherwise specified, all tables and listings in this section will be based on the randomized set, and all summaries and data listings will use treatment labels as specified in [Section 3.3](#). Subjects will be analyzed according to the treatment they were randomized to receive.

5.1. Disposition

The number of subjects in each of the sets will be summarized. All subjects screened will be presented overall and the Randomized set, ITT set, and Safety set will be summarized overall and by treatment group using the all subjects screened set.

A summary of the subjects excluded from each analysis set and the reasons for exclusion will be presented using the Randomized set. This summary will include the number and percentage of subjects for the following categories: subjects excluded from the ITT set and reasons, and subjects excluded from the Safety set and reasons. Percentages for exclusion reasons will be based on the number of subjects excluded from the specific analysis set being summarized. Subjects could be excluded from an analysis set for more than one reason. A listing of subjects included in any analysis set as well as a listing of subjects excluded from any analysis set will be produced.

The number of subjects by country will be summarized by treatment group and overall.

A summary of subject status and reason for study withdrawal will be provided. The status section will display:

For Part A:

- Subjects who attended the Week 52 Visit with the following subcategories:
 - Did not enter Part B, defined as subjects who completed week 52 visit and did not enter Part B
 - Completed Safety Follow-up
 - Not Completed Safety Follow-up
 - Enter Part B, defined as subjects who were enrolled in Part B
- Early withdrawal or study termination:
 - Early withdrawal, is defined as subjects who permanently discontinued SC IP and prednisone study drug treatments prior to completing week 52 visit AND withdrew from the study.
 - Study termination is defined as subjects who were still in the study as of study termination date of 10 Oct 2017.

This includes the following subcategory:

- Completed Safety Follow-up, defined as the 16 week safety follow up after withdrawal or study termination
- Not Completed Safety Follow-up

For Part B:

- Completed Week 104 visit, defined as subjects who completed Part B
 - Completed Safety Follow-up
 - Not Completed Safety Follow-up
- Early withdrawal or Study Termination with the following subcategory:

- Completed Safety Follow-up, defined as subjects who attended the safety follow up period after withdrawal or study termination
- Not Completed Safety Follow-up

The reasons for study withdrawal will also be summarized within this table for each Part of the study. The reasons for study withdrawal will be presented in the order they are displayed in the eCRF.

The following information will be summarized on the Safety Set on a separate table:

- Subjects who completed SC IP treatment:
 - Prednisone study drug treatment completed
 - Permanently discontinued prednisone study drug treatment prior to completing week 52 visit
- Subjects who permanently discontinued SC IP treatment prior to completing week 52 visit (this will include subjects who discontinue SC IP due to study termination)
 - Prednisone study drug treatment discontinued prior to completing week 52 visit
 - Completed prednisone study drug treatment

Treatment status and reason for discontinuation will be provided for SC IP (sirukumab or placebo) and prednisone study drug separately. Reasons for study treatment discontinuation will be presented in the order they are displayed in the eCRF. Listings of discontinuation of IP SC and prednisone study drug will be generated. The listings will include last dose date, and reasons for study treatment discontinuation.

A listing of reasons for study withdrawal will be generated. A listing of subjects continuing into Part B of the study will be produced.

Listings of planned and actual treatments for subjects, and of all subjects for whom the treatment blind was broken will be generated.

Subjects will be assigned to the actual treatment groups if they received:

Subcutaneous IP for more than 50% of their injections	Prednisone study drug for more than 50% of the doses	Actual treatment
S100	3m	B
	6m	A
	12m	A
	random	A
S50	3m	C
	6m	C
	12m	C
	random	C
Placebo	3m	D
	6m	D
	12m	E
	random	E

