4.2. Randomization, Stratification and Blinding

Central randomization will be implemented in this study. Subjects will be randomized in a ratio of 3:3:2:2:2 and assigned to 1 of 5 treatment arms in accordance with the computer-generated randomization schedule generated prior to the start of the study, using validated software. Randomization will be performed by an Interactive Response Technology System. Once a randomization number has been assigned to a subject, it will not be re-assigned.

Randomization will be stratified by baseline oral prednisone dose (<30 mg/day or ≥ 30 mg/day). The number of relapsing/refractory subjects will be capped at approximately 50% to ensure that a sufficient number of subjects with new onset disease are recruited.

Blinding will be maintained during the 52-week double-blind treatment phase of this study by the provision of sirukumab and matching placebo for sirukumab in prefilled syringes in a matching presentation. Blinding to the prednisone dose during the taper will be maintained by providing prednisone doses below 20 mg in numbered blister packs. Depending on the subject's assignment to either the 3-, 6-, or 12-month taper, the over-encapsulated dose may or may not contain prednisone. The blister packs contain a combination of over-encapsulated 10 mg, 5 mg, and/or 1 mg prednisone tablets with cellulose filler to prevent rattling and/or placebo capsules containing only the filler. Each subject, regardless of treatment arm, will be provided the same number of capsules per day for a given week to maintain the blind.

Blinding during the q4w dosing regimen will be maintained by the provision of placebo for sirukumab such that subjects randomized to this arm will follow a q2w dosing regimen but alternate between active (starting at Baseline) and placebo treatments for the duration of the 52-week, double-blind phase.

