4.3.4. Safety

The Safety set will include all randomized subjects who received at least 1 dose of SC IP. All subjects in the Safety set will be analyzed according to the treatment actually received and not according to the treatment they were randomized to receive, in the event there is a discrepancy. The Safety set will be used to analyze all of the safety endpoints.

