7.2.2.1. Subcutaneous IP

Overall treatment compliance with SC IP will be assessed by the number of injections actually received versus the number of injections planned. The percentage compliance with SC IP will be calculated as: $100 \times (\text{number taken}/\text{number planned})$. Subjects randomized to SC IP 50 mg q4w take SC IP injections 1 week, and placebo injections 2 weeks later in order to provide blinding from those taking 100 mg q2w. For these subjects, compliance will be calculated irrespective of whether the injection was a placebo or sirukumab dose. The number of planned injections will be calculated based on the subject's last visit.

For example, if a subject's last visit = Week 20, then the planned number of injection will be 11. If this subject only reports 10 injections, the percentage compliance with SC IP will be $100 \times (10/11) = 90.9\%$.

Overall SC IP compliance and compliance categories (0; >0% and <80%; ≥80% and ≤120%; >120%) will be summarized for each treatment group. Compliant subjects (i.e. subjects with a compliance between ≥80% and ≤120%) will be summarized.

In addition, the SC IP / placebo administration will be summarized by treatment groups as following:

- Percentage of subjects who received all SC IP injections
- Percentage of subjects who missed at least 1 SC IP injection

- Percentage of subjects who missed 1/2/3/4/5/6, or more SC IP injections

All SC IP compliance data will be listed.

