All safety analyses will be performed on the Safety set. Subjects will be analyzed according to the treatment actually received, regardless of the treatment group they were randomized to. Percentages for safety summaries based on the number of subjects with a given event or attribute will be based on Safety set. All safety data will be included in listings.

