The proportions of subjects with AESIs and relative risks for the six comparisons will be summarized in a table. This will be done using the RELRISK option of the table statement of the SAS PROC FREQ procedure.

A supportive listing of all AESI will be presented.

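### Does the more-than-half rule for actual treatment misplace Arm C subjects, since half of their scheduled injections are placebo?

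*SAP*

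**What the plan says.** The table at the end of SAP 5.1 crosses two majority rules to give the actual group. One is the SC product received as "Subcutaneous IP for more than 50% of their injections" (S100, S50 or Placebo). The other is the prednisone taper received for more than half of the doses (3m, 6m, 12m or random). S50 with any taper gives Arm C; Placebo with the 3m or 6m taper gives Arm D. The labels are not defined, and the SC column has no row for a subject with no majority.

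SAP 4.2 states that Arm C subjects "alternate between active (starting at Baseline) and placebo treatments for the duration of the 52-week, double-blind phase". SAP 7.2.2.1 says how those injections count for compliance: "compliance will be calculated irrespective of whether the injection was a placebo or sirukumab dose". No equivalent sentence appears in SAP 5.1.

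SAP 4.3.4 analyses the Safety set "according to the treatment actually received and not according to the treatment they were randomized to receive, in the event there is a discrepancy". The opening of SAP section 9 says: "Subjects will be analyzed according to the treatment actually received, regardless of the treatment group they were randomized to". For Part B, SAP 11.1.2 has subjects "analyzed according to the treatment actually received in Part A and not according to the treatment they were randomized to receive in Part A", and also limits this to cases of discrepancy.

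**The concern.** Arm C is the one arm whose correct treatment sits on the 50% threshold by design. If a programmer counts each syringe by what it contained, whether a fully adherent subject gets a group depends on whether the number of injections is even or odd. A compliant subject who misses an active dose can be tabulated as placebo.

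The actual group feeds every Part A safety table, the exposure-adjusted rates and the Part B safety tables. It also feeds the relative risks: "The proportions of subjects with AESIs and relative risks for the six comparisons will be summarized in a table". Take the six to be the primary and the five secondary contrasts in SAP 2.1. Moving one subject from C to D then touches four of them (A–D, B–D, C–D and C–E), and both sides of C–D. After termination, efficacy is reported by summary statistics only, so the safety tables carry much of the report.

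**Working it through.** **The plan's own count.** SAP 7.2.2.1 gives 11 planned injections for a last visit at Week 20. Dosing every 2 weeks from Week 0 gives X/2 + 1 = 20/2 + 1 = 11, which agrees. The example goes on: "If this subject only reports 10 injections, the percentage compliance with SC IP will be" 90.9%, and 100 × 10/11 = 90.9.

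**Reading 1: by content.** Assume that a missed dose does not shift the alternation. With active first, n injections on schedule contain ceil(n/2) active and floor(n/2) placebo. Footnote 3 to SAP Table 10 limits Week 52 dispensing to subjects starting open-label drug, so a full blinded course is Weeks 0 to 50, or 26 injections. The X/2 + 1 convention gives 27.

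| Case | Active / placebo | Majority | Group |
|---|---|---|---|
| 26 on schedule | 13 / 13 | none (50.0%) | none |
| 27 on schedule | 14 / 13 | active 51.9% | C |
| 26, one active missed | 12 / 13 | placebo 52.0% | D |
| 26, one placebo missed | 13 / 12 | active 52.0% | C |
| 11 on schedule | 6 / 5 | active 54.5% | C |
| 11, one active missed | 5 / 5 | none (50.0%) | none |
| 11, one placebo missed | 6 / 4 | active 60.0% | C |

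The documents give no rate of missed injections. The next figures assume independent misses, by exact binomial enumeration, as no group / D / C:

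- 26 scheduled: 100% / 0% / 0% at no misses; 63% / 18% / 18% at 2%; 40% / 30% / 30% at 5%; 27% / 36.5% / 36.5% at 10%.
- 27 scheduled: 0% / 0% / 100% at no misses; 23% / 9% / 68% at 5%; 22% / 17.5% / 61% at 10%.

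**Reading 2: by regimen.** Every kit dispensed to an Arm C subject belongs to the 50 mg q4w regimen, so the S50 share is n/n = 100% for any number taken and any pattern of misses. All go to C.

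**Which reading the table supports.** Apply the content rule to the prednisone column. In SAP Table 3 the 3-month blinded taper is 15, 10, 5, 3 and 1 mg, then 0. The blinded capsule schedule in SAP 7.2.2.2 runs 45 weeks.

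- 3-month: 5/45 = 11.1% of blinded weeks are non-zero. Adding the longest open-label stretch (7 weeks, 60 down to 20 mg) gives 12/52 = 23.1%.
- 6-month: 19/45 = 42.2% of blinded weeks are non-zero.

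By content, an Arm B subject who completed the capsule schedule would have mostly 0 mg doses. The table has no row for those, and its random row would send S100 to Arm A. A count of blinded weeks would likewise send Arm D completers to Arm E. So 3m, 6m and 12m must name the schedule a dose belongs to, and S100, S50 and Placebo in the next column most naturally name the SC regimen. SAP 5.1 itself, just above the table, uses SC IP to cover sirukumab or placebo.

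**Whether the rule is reached at all.** Under SAP 4.3.4 actual treatment replaces the randomized arm only where they differ. For an Arm C subject given only Arm C kits they do not. Section 9 states that its analyses use the Safety set, so that condition carries over.

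**The case for a change.** The best case for a change runs as follows. The rule counts injections, and SAP 7.2.2.1 itself distinguishes Arm C's active and placebo injections by content, then needs a sentence to pool them for compliance. That sentence cannot be carried silently into SAP 5.1. The SC column lacks the random row that the prednisone column has. SC treatment codes are opened after database lock, so the reading would be applied with the codes in view. A clarifying line costs little.

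What stands is that S50 is undefined and that exactly 50% has no row. The rest is weaker. The content reading would leave every Arm C subject with 26 injections on schedule without a group, and in the neighbouring column it would break Arms B and D, so it is not a serious rival. Under the regimen reading a tie needs exactly half of a subject's injections to come from another arm's kits, a dispensing failure that would be handled individually under any rule. An error would also be visible. SAP 5.1 calls for a listing of planned and actual treatments and for Safety set counts by group and overall. An ungrouped subject would make the groups fall short of the total, and a C subject shown as D would appear in the listing.

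Extra wording carries its own risk. Suppose the blinding placebo were left out of the count only for subjects randomized to Arm C. A subject from another arm given the full Arm C sequence would then have 13/26 and 13/26 and revert to the randomized arm, although an as-treated rule exists for exactly that case.

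**Conclusion.** No change follows. This is an unwritten definition and an empty cell that an analyst would fill correctly from the table itself. On the regimen reading the number of Arm C subjects misplaced is zero, whatever the injection count or missed doses. The ties and moves to Arm D arise only from a content count that the prednisone labels rule out in practice.

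The conclusion rests on two assumptions: that S50 denotes the alternating 50 mg and placebo regimen, and that dispensed kits can be traced to a regimen. The documents do not give Arm C's size at termination (34 was planned) or the pattern of missed injections. The number affected under the content reading, and the direction of any bias, therefore cannot be stated. Any effect would be confined to the as-treated safety outputs of Parts A and B; efficacy and disposition by randomized arm would not move.
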